14.1.2. Sample Size for Key Secondary Rate of Change in eGFR Endpoints

Data from IgAN database from the University of Leicester, UK, provides the basis for the power calculation for eGFR Rate of Decline over 2 years in patients with a baseline UPE ≥ 2 g/day. Patients on ACE/ARBs with a baseline UPCR of ≥ 2 g/day were identified and their eGFR values over 3 to 24 months were assigned to 3 monthly windows to reflect the intended sampling schedule in the OMS721-IGA-001 protocol.

The annualized eGFR rate of decline was thus estimated to be -5.44 mL/min/m 2 (SE 0.1869 mL/min/m 2), the between slope variance component $\sigma\varphi^2$ was estimated to be 6.4932 2 mL/min/m 2 annually ($= 0.7356^2$ mL/min/m 2 monthly), and the residual error variance $\sigma\varrho^2$ was estimated to be $= 6.5077^2$ mL/min/m 2 .

Thus, hypothesizing that the 2-year annualized eGFR rate of decline for narsoplimab relative to placebo in the high-risk proteinuria group (baseline UPE ≥ 2 g/day) is 3.48 mL/min/1.73 m 2 , a sample size of 280 patients (i.e., 140 per treatment group) followed for 2 years post randomization will provide at least 85% power at the 2-sided 5% level to test this hypothesis.

Similarly, data from the University of Leicester registry provide an estimate of the annualized eGFR rate of decline in patients with a baseline UPCR of > 1 g/day of -4.40 mL/min/m 2 (SE 1.716 mL/min/m 2), and the between-slope variance component $\sigma\varphi^2$ was estimated to be 7.8469 2 mL/min/m 2 annually ($= 0.6539^2$ mL/min/m 2 monthly) with the residual-error variance $\sigma\varrho^2$ estimated to be $= 5.9517^2$ mL/min/m 2 .

Hypothesizing that the 2-year annualized eGFR rate of decline for narsoplimab relative to placebo in the all-patients population is 2.45 mL/min/1.73 m 2 , a sample size of 450 patients (i.e., 225 per treatment group) followed for 2 years post randomization will provide at least 85% power at the 2-sided 5% level to test this hypothesis.

CONFIDENTIAL

No use, disclosure, or reproduction outside of Omertos without prior written authorization

14.1.3. Blinded Sample Size Re-estimation for UPE Endpoint

A pre-planned blinded sample size re-estimation for UPE endpoint in the all-patients population was performed when 168 patients completed the Week 36 visit. The independent IDMC statistician re-calculated the sample size using an adjusted variance. A bias-adjusted variance of the log-transformed 24-hour UPE change from baseline to Week 36 was calculated using the pooled variance from the available data and the assumed treatment effect size in a blinded fashion. The bias-adjusted variance was expressed as [Kieser 2003]:

$$\frac{VV^2}{aaaaaa} = \frac{VV^2}{pppppppeaa} - \frac{\frac{mm}{4(mm-1)} \Delta^2}{mm},$$

where $VV^2_{pppppppeaa}$ is the pooled variance, n is half of the number of patients with UPE at Week 36 at the time of the sample size re-estimation (i.e., m = 168), and Δ is the assumed treatment effect size in the sample size calculation.

The log scale SD was estimated to be lower than anticipated and, hence, no change to sample size was made.

14.1.4. Statistical and Analytical Plans

The statistical and analytical plans presented below summarize the more complete plans to be detailed in the statistical analysis plan (SAP). A change to the data analysis methods described in the protocol will require a protocol amendment only if it alters a principal feature of the protocol. The SAP will be finalized prior to the interim database snapshot. Any changes to the methods described in the final SAP will be described and justified in the clinical study report.

14.1.5. Conditional Power-Based Sample Size Re-Estimation for Key Secondary eGFR Rate-of-Change Endpoint in the High-Risk Proteinuria Group (i.e., Patients with Baseline Proteinuria $\geq 2\text{g/day}$)

A CP-based sample size re-estimation for the key secondary eGFR Rate-of-Change endpoint in patients in the high-risk proteinuria group is planned at the time of the formal interim analysis of the primary UPE endpoint in the same population. The method will be described in the final SAP.

14.1.6. General Considerations

Summary statistics for continuous variables will include number of patients, mean, median, standard deviation, minimum, and maximum. For categorical variables, frequencies and percentages will be provided. When required for the statistical analysis of a particular variable, the baseline value will be the last recorded value prior to randomization. The exception is the baseline 24-hour UPE, uPCR and uACR, which are defined as the average of the two pre-dose values collected during the last two weeks of the Run-In Period before randomization. In addition, study week is defined from study Day 1 and will be determined by analysis visit windows which are defined approximately equally over adjacent scheduled visits. A study endpoint at a particular study week (e.g., 24-hour UPE at 36 weeks) is the value collected during that analysis visit window. All statistical tests will be performed at the two-sided significance level of 5%. All confidence intervals will be constructed at the two-sided 95% confidence level.

CONFIDENTIAL

No use, disclosure, or reproduction outside of Omertos without prior written authorization

14.1.6.1. Adjustments for Covariates

Efficacy analyses will adjust for randomization strata. Some potential baseline patient and disease characteristics may affect the interpretation of the efficacy results. Subgroup analyses and regression analyses may be performed to adjust for the potential covariate effects. These analyses will be considered exploratory and, if performed, will be discussed in the clinical study report.

14.1.6.2. Multicenter Study

This is a multicenter study. Descriptive statistics of the primary efficacy endpoint will be provided for each site to evaluate potential site differences.

14.1.6.3. Multiple Comparisons and Multiplicity

The primary efficacy endpoint (change in log-transformed 24-hour UPE from baseline to 36 weeks) in the high-risk proteinuria group and, if positive, the two key secondary endpoints will be tested sequentially to preserve the overall type I error rate of 5%.

Key Secondary Efficacy Endpoints:

- i. the rate of change in eGFR over 2 years in the high-risk proteinuria group
- ii. the rate of change in eGFR over 2 years in the all-patients population

If the primary efficacy endpoint is statistically significant at 5% level in a 2-sided test, then key secondary endpoint (i), the rate of change in eGFR over 2 years in the high-risk proteinuria group, will be tested in a two-sided test at 5% level of significance. If the key secondary eGFR endpoint for the high-risk proteinuria group is statistically significant in a two-sided test at 5% level, then the key secondary eGFR endpoint (ii), the rate of change in eGFR over 2 years in the all-patients population, will be tested in a two-sided test at 5% level.

Testing of other efficacy endpoints will not be subject to type-1 error control and, therefore, will be viewed as supportive.

In the blinded SSRE for the key secondary UPE endpoint (primary endpoint in the original protocol), no alpha level penalty was applied.

A conditional power-based SSRE for the key secondary endpoint of eGFR is planned in the high-risk proteinuria group (at least $N = 180$) at the time of the primary endpoint analysis. At this SSRE, no formal statistical testing will be performed on eGFR data.

14.1.6.4. Handling of Missing Data

The following general methods will be used for producing the data summaries and documenting missing data:

- Available clinical data at each visit will be presented and the sample size displayed will reflect the number of patients with available data. Patient listing data will be provided as recorded on the case report form, indicating partial dates and missing data

CONFIDENTIAL

No use, disclosure, or reproduction outside of Omertos without prior written authorization

- Generally, if data are missing or incomplete, the missing or incomplete values will be presented in the data listings. Data summaries will be based on the observed data without imputation, unless otherwise specified
- If there are 2 or more assessments in the same analysis visit, the closest one to the target day will be used in the analysis. If there are 2 assessments that are equally spaced from the target day, the latest one will be used in the analysis, unless otherwise specified

14.1.6.5. Analysis Populations

The primary efficacy analysis population will be the Full Analysis Set (FAS) population, defined as all randomized patients in the high-risk proteinuria group. Patients will be grouped by their assigned treatment. When considering the all-patients population (baseline 24-hour UPE > 1 g/day), the same principal applies, i.e. the FAS for this population is defined as all randomized patients.

The supporting efficacy analysis populations will be the Per-Protocol Analysis Set population, which includes all randomized high-risk proteinuria patients who receive at least 10 doses of study drug in the Initial Treatment Period and have non-missing primary endpoint data (24-hour UPE at baseline and Week 36). Patients will be grouped by their assigned treatment.

Safety analyses will be based on the Safety Analysis Set, which includes all patients who receive any positive amount of study drug. Patients will be grouped by their actual treatment received. Supportive safety summaries will also be made in the population of all patients who receive any positive amount of study drug.

14.1.7. Patient Disposition

An accounting of study patients by disposition will be tabulated by treatment group. The number of patients in each analysis population will be summarized by treatment group. Patients who discontinued study drug prematurely or withdrew from the study will be summarized and listed with reason for early termination/withdrawal. Patients who re-initiated study treatment will be summarized by treatment group.

Furthermore, the number of patients who receive open-label treatment of narsoplimab will be summarized by treatment group for the FAS population. Time from randomization to the date of the first dose of open-label narsoplimab will be analyzed by Kaplan-Meier (KM) method for each treatment group for the FAS population. Patients who have not received open-label narsoplimab-treatment will be censored at the last known date on study. Median time with 95% confidence interval will be provided by treatment group.

14.1.8. Patient Characteristics

Demographic and other baseline characteristics and concomitant medications will be listed and summarized by treatment group.

14.1.9. Treatment Compliance

Because all dosing will be under direct supervision of study personnel, treatment compliance will not be analyzed. Dosing information will be summarized and listed.

CONFIDENTIAL

No use, disclosure, or reproduction outside of Omertos without prior written authorization

14.1.10. Efficacy Analyses

14.1.10.1. Analysis of Primary Efficacy Endpoint

The primary efficacy endpoint will be based on the natural logarithm transformed 24-hour UPE. Descriptive statistics for the log-transformed 24-hour UPE change from baseline to 36 weeks, the geometric mean ratio (GMR) relative to the study baseline, and the coefficient of variation in percentage will be provided by treatment group for the FAS population.

The primary analysis will be a MMRM analysis on the change from baseline in log-transformed 24-hour UPE at Week 12, Week 24, Week 30, and Week 36. The model will be fitted in SAS via the PROC MIXED procedure. Terms will be included for treatment, time (as a categorical variable for the four timepoints), treatment by time interaction, and randomization strata as fixed effects. Within patient error will be modeled using an unstructured covariance matrix. Log baseline UPE will be included as a covariate in the model. Restricted maximum likelihood method will be used to estimate the model parameters. If the estimation of the model fails, an autoregressive (1) [AR(1)] covariance structure will be used. The difference in least squares (LS) means at Week 36 between the treatment groups and its 95% confidence interval (CI) will be estimated. Two-sided p-value will be calculated. The LS mean at Week 36 will be estimated with 95% CI for each treatment group. The ratio of the GMR between the treatment groups will also be estimated with 95% CI.

Sensitivity analysis of the primary efficacy endpoint relate to the handling of missing data.

Jump to Placebo Multiple Imputation

The first approach will employ a control-based multiple imputation [Ratitch 2011] whereby missing observations in both the narsoplimab and placebo groups are imputed using only data observed in the placebo group; as such, this approach reflects a 'jump to placebo (or reference)' analysis. Imputation of values in the placebo arm will assume missing at random (MAR) while imputation of values in the narsoplimab arm will assume missing not at random (MNAR), i.e. as if the patient had been a member of the placebo arm. This approach does not assume a sustained benefit of narsoplimab treatment after discontinuation and limits a post-discontinuation effect to that of placebo.

Tipping Point Multiple Imputation

The second approach analysis will be a tipping point analysis. This will assess the robustness of the primary endpoint analysis by determining the penalty that, when applied to narsoplimab patients with missing data, renders the primary endpoint p-value non-significant. This analysis requires that the data has a monotone missingness pattern, thus, and as necessary, a partial-imputation method using the MCMC method will be employed as described above for Jump to Placebo.

COVID-19

Statistical analysis using the primary analysis method will be performed by excluding the data collected from patients re-initiating study treatment due to the COVID-19 pandemic.

CONFIDENTIAL

No use, disclosure, or reproduction outside of Omersa without prior written authorization

14.1.10.2. Analysis of Rate of Change in eGFR

The analysis of the key secondary efficacy eGFR endpoints (1) the rate of change in eGFR over 2 years in the high-risk proteinuria group and (2) the rate of change in eGFR over 2 years in the all-patients population will be performed only if the primary UPE efficacy endpoint in the high-risk proteinuria group is significant at 5% level of significance in a 2-sided test. If the primary endpoint is significant then key secondary endpoints (1) and (2) will each be sequentially tested at 5% level of significance in a 2-sided test.

The key secondary rate of change in eGFR over 2 years in patients in the high-risk proteinuria group (baseline UPE $\geq 2\text{g/day}$) and in the all-patients population will be analyzed by a random coefficients model for the FAS population. This analysis will be performed after the final database lock.

The random coefficients model is specified as follows:

$$yy_{iiaa} = (\beta\beta_0 + bb_{0ii}) + \beta\beta_1 \cdot GG + (\beta\beta_2 + bb_{2ii})xx_{iiaa} + \beta\beta_3 \cdot GG \cdot xx_{iiaa} + ee_{iiaa}$$

where

- yy_{iiaa} is the eGFR value for patient ii at assessment time jj ;
- xx_{iiaa} is the time of the jj^{th} assessment for patient ii ;
- $GG = 0, 1$ for placebo and narsoplimab
- $\beta\beta_0$ = intercept fixed placebo effect, $\beta\beta_0 + \beta\beta_1$ = intercept fixed narsoplimab effect and $\beta\beta_1$ = the fixed treatment effect on the intercept;
- $\beta\beta_2$ = slope fixed placebo effect, $\beta\beta_2 + \beta\beta_3$ = slope fixed narsoplimab effect and $\beta\beta_3$ = the fixed treatment effect on slope;
- bb_{0ii} and bb_{2ii} are the random intercept and slope effects associated with patient ii ;
- ee_{iiaa} are the residual error for patient ii at time jj , with ee_{iiaa} ;

The random effects, bb_{0ii} and bb_{2ii} are assumed $ii. ii. dd$ Normally distributed with variance components $\sigma\sigma_0^2$ and $\sigma\sigma_2^2$ and, independently, the random error ee_{iiaa} is Normally distributed with variance $\sigma\sigma^2$.

The restricted maximum likelihood (REML) method in SAS PROC MIXED will be used to fit the model. The treatment difference in the rate of change in eGFR over 2 years will be estimated from the model along with its standard error, 2-sided confidence interval and p-value. The applicable alpha level will be 5% in a 2-sided test.

Sensitivity analyses for both key secondary efficacy eGFR endpoints will include:

- Jump to Placebo Multiple Imputation
- Tipping Point Multiple Imputation
- COVID-19

CONFIDENTIAL

No use, disclosure, or reproduction outside of Omertos without prior written authorization

These analyses will be executed in the same fashion as described for the primary UPE endpoint.

14.1.10.3. Analyses of Secondary and Exploratory Efficacy Endpoints

Proteinuria durability will be evaluated by the time adjusted AUC change from baseline in the log-transformed 24-hour UPE between 36 and 48 weeks, and between 36 and 72 weeks. The time adjusted AUC will be calculated as the AUC of the change in the log-transformed 24-hour UPE from baseline over the said time period divided by the time between the first observation and the last observation over the said time period. Patients who are on study and have not reached the Week-36 visit will be excluded from the analysis. The time adjusted AUC will be summarized descriptively. The geometric mean ratio relative to the study baseline, and the coefficient of variation in percentage will be provided by treatment group for the FAS population. A MI with FCS regression method will be used to impute missing log-transformed 24-hour UPE at the scheduled visits from Week 12 to Week 72. The FCS regression method will include the treatment group and the randomization strata as covariates. The time adjusted AUC will be calculated using the imputed values. The treatment difference will be estimated by an analysis of variance (ANOVA) model with treatment and randomization strata as covariates using Rubin method with 30 imputations.

Proteinuria responder durability will be evaluated by the time adjusted AUC 24-hour UPE from 36 weeks to 48 weeks where this time adjusted AUC is < 1 g/day or at least 50% reduced from the baseline 24-hour UPE for the high proteinuria group in the FAS population. Patients who are on study and have not reached the Week-36 visit will be excluded from the analysis. The time adjusted AUC will be calculated using AUC similar to the above. Patients with missing time average will be considered as non-responders (non-responder imputation). Percentage of proteinuria responder durability will be summarized by treatment group. A CMH test stratified by the baseline eGFR level (≥ 30 to ≤ 45 mL/min/1.73 m² and > 45 mL/min/1.73 m²) will be performed. Proteinuria responder durability will also be evaluated similarly by the time adjusted AUC 24-hour UPE from 36 weeks to 72 weeks.

Natural logarithm transformation will be used to analyze 24-hour UPE, 24-hour uPCR, 24-hour uACR, spot-urine uPCR and spot-urine uACR. Geometric-mean ratio relative to the study baseline will be presented by treatment group and visit for the FAS population. A repeated measures model for the change in the log-transformed value from baseline will be used for analysis. The model will include treatment, time (as a categorical variable for the scheduled timepoints), treatment by time interaction, randomization strata as fixed effects and a time-dependent covariate for open-label treatment of narsoplimab as fixed effects, and an AR (1) covariance matrix. The time-dependent covariate is a binary variable that has a value of 0 before the initiation of the open-label treatment and 1 afterwards. It is defined for the placebo group only. The REML method will be used to estimate the model parameters. The difference in least squares (LS) means between the treatment groups and its 95% CI will be estimated for each post-baseline scheduled visit. The LS mean will be estimated with 95% CI for each treatment group. The ratio of the GMR between the treatment groups will also be estimated with 95% CI. It is noted that the primary analysis of 24-hour UPE is based on the 24-hour UPE up to Week 36 and the time-dependent covariate is not applicable to the primary analysis.

Time adjusted AUC change from baseline in spot-urine uPCR through 36 weeks will be calculated as the AUC of the change from baseline in spot-urine uPCR divided by the time from

CONFIDENTIAL

No use, disclosure, or reproduction outside of Omeros without prior written authorization

baseline to the last observation on or before Week 36. Time average of change in spot-urine uPCR will be summarized descriptively. An ANOVA model with treatment and randomization strata as covariates will be performed.

The binary endpoints will be summarized descriptively. Non-responder imputation will be used to impute missing data. Exact 95% confidence intervals for the crude rate will be calculated and a CMH test stratified by the randomization stratum will be performed for the FAS population.

The time-to-event endpoints will be analyzed by Kaplan-Meier (KM) method for each treatment group for the FAS population. Median time with 95% confidence interval will be provided by treatment group. Log-rank test stratified by the randomization stratum will be performed.

Change from baseline in RBC/HPF will be summarized descriptively by treatment group and scheduled visit.

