- Time-averaged change from baseline in the log-transformed 24-hour UPE between 36 weeks and 72 weeks in patients with ≥ 2 g/day UPE at baseline (high-risk proteinuria group)
- Time-averaged change from baseline in the log-transformed 24-hour UPE between 36 weeks and 48 weeks in the all-patients population
- Time-averaged change from baseline in the log-transformed 24-hour UPE between 36 weeks and 72 weeks in the all-patients population

Safety and Other Endpoints

- Safety and tolerability of narsoplimab for the treatment of IgAN as assessed by AEs, vital signs, clinical laboratory tests, and ECGs
- Change from baseline in log-transformed 24-hour uPCR over time in patients with baseline 24-hour UPE ≥ 2 g (high-risk proteinuria group)
- Achievement of $\geq 50\%$ reduction from baseline in 24-hour UPE at 36 weeks in patients with baseline 24-hour UPE ≥ 2 g (high-risk proteinuria group)
- Achievement of $\geq 30\%$ reduction from baseline in 24-hour UPE at 36 weeks in patients with baseline 24-hour UPE ≥ 2 g (high-risk proteinuria group)
- Change from baseline in log-transformed 24-hour uPCR over time in the all-patients population
- Achievement of $\geq 50\%$ reduction from baseline in 24-hour UPE at 36 weeks in the all-patients population
- Achievement of $\geq 30\%$ reduction from baseline in 24-hour UPE at 36 weeks in the all-patients population
- Time averaged change from baseline in the log-transformed 24-hour uPCR through 36 weeks in patients with baseline 24-hour UPE ≥ 2 g (high-risk proteinuria group)
- Achievement of partial proteinuria remission defined as 24-hour UPE < 0.6 g at any time post baseline in patients with baseline 24-hour UPE ≥ 2 g (high-risk proteinuria group)

CONFIDENTIAL

No use, disclosure, or reproduction outside of Omersus without prior written authorization

- Achievement of complete proteinuria remission defined as 24-hour UPE < 0.3 g at any time post baseline in patients with baseline 24-hour UPE ≥ 2 g (high-risk proteinuria group)
- Time averaged change from baseline in the log-transformed 24-hour uPCR through 36 weeks in the all-patients population
- Achievement of partial proteinuria remission defined as 24-hour UPE < 0.6 g at any time post baseline in the all-patients population
- Achievement of complete proteinuria remission defined as 24-hour UPE < 0.3 g at any time post baseline in the all-patients population

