7.2.4. Safety and Other Endpoints

- Safety and tolerability of narsoplimab for the treatment of IgAN as assessed by AEs, vital signs, clinical laboratory tests, and ECGs
- Change from baseline in log-transformed 24-hour uPCR over time in patients with baseline 24-hour UPE ≥ 2 g (high-risk proteinuria group)
- Achievement of a $\geq 50\%$ reduction from baseline in 24-hour UPE at 36 weeks in patients with baseline 24-hour UPE ≥ 2 g (high-risk proteinuria group)
- Achievement of $\geq 30\%$ reduction from baseline in 24-hour UPE at 36 weeks in patients with baseline 24-hour UPE ≥ 2 g (high-risk proteinuria group)
- Change from baseline in log-transformed 24-hour uPCR over time in the all-patients population
- Achievement of $\geq 50\%$ reduction from baseline in 24-hour UPE at 36 weeks in the all-patients population
- Achievement of $\geq 30\%$ reduction from baseline in 24-hour UPE at 36 weeks in the all-patients population
- Time-averaged change from baseline in the log-transformed 24-hour urine protein/creatinine ratio (uPCR) through 36 weeks in patients with baseline 24-hour UPE ≥ 2 g (high-risk proteinuria group).
- Achievement of partial proteinuria remission defined as 24-hour UPE < 0.6 g at any time post baseline in patients with baseline 24-hour UPE ≥ 2 g (high-risk proteinuria group)
- Achievement of complete proteinuria remission defined as 24-hour UPE < 0.3 g at any time post baseline in patients with baseline 24-hour UPE ≥ 2 g (high-risk proteinuria group)

CONFIDENTIAL

No use, disclosure, or reproduction outside of Omertos without prior written authorization

- Time averaged change from baseline in the log-transformed 24-hour uPCR through 36 weeks in the all-patients population
- Achievement of partial proteinuria remission defined as 24-hour UPE < 0.6 g at any time post baseline in the all-patients population
- Achievement of complete proteinuria remission defined as 24-hour UPE < 0.3 g at any time post baseline in the all-patients population
- Use of rescue therapy for IgAN at any time post baseline in the all-patients population and in patients with baseline 24-hour UPE ≥ 2 g (high-risk proteinuria group)
- Change from baseline in eGFR at 36 weeks in the all-patients population and in patients with baseline 24-hour UPE ≥ 2 g (high-risk proteinuria group)
- Pharmacokinetics and pharmacodynamics of narsoplimab
- Occurrence of ADA and, if present, neutralizing antibody (NAb)

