### Tertiary Endpoints

- Change from baseline in log-transformed 24-hour uPCR over time in patients in the high-risk proteinuria group (baseline 24-hour UPE  $\geq 2$  g/day)
- Achievement of  $\geq 50\%$  reduction from baseline in 24-hour UPE at 36 weeks in patients in the high-risk proteinuria group (baseline 24-hour UPE  $\geq 2$  g/day)
- Achievement of  $\geq 30\%$  reduction from baseline in 24-hour UPE at 36 weeks in patients in the high-risk proteinuria group (baseline 24-hour UPE  $\geq 2$  g/day)
- Change from baseline in log-transformed 24-hour uPCR over time in patients in the all-patients population (baseline 24-hour UPE  $> 1$  g/day)
- Achievement of  $\geq 50\%$  reduction from baseline in 24-hour UPE at 36 weeks in patients in the all-patients population (baseline 24-hour UPE  $> 1$  g/day)
- Achievement of  $\geq 30\%$  reduction from baseline in 24-hour UPE at 36 weeks in patients in the all-patients population (baseline 24-hour UPE  $> 1$  g/day)
- Time averaged change from baseline in the log-transformed 24-hour uPCR through 36 weeks in patients in the high-risk proteinuria group (baseline 24-hour UPE  $\geq 2$  g/day)
- Achievement of partial proteinuria remission defined as 24-hour UPE  $< 0.6$  g at any time post baseline in patients in the high-risk proteinuria group (baseline 24-hour UPE  $\geq 2$  g/day)
- Achievement of complete proteinuria remission defined as 24-hour UPE  $< 0.3$  g at any time post baseline in patients in the high-risk proteinuria group (baseline 24-hour UPE  $\geq 2$  g/day)
- Time averaged change from baseline in the log-transformed 24-hour uPCR through 36 weeks in patients in the all-patients population (baseline 24-hour UPE  $> 1$  g/day)

- Achievement of partial proteinuria remission defined as 24-hour UPE  $< 0.6$  g at any time post baseline in patients in the all-patients population (baseline 24-hour UPE  $> 1$  g/day)
- Achievement of complete proteinuria remission defined as 24-hour UPE  $< 0.3$  g at any time post baseline in patients in the all-patients population (baseline 24-hour UPE  $> 1$  g/day)
- Use of rescue therapy for IgAN at any time post baseline in patients in the all-patients population (baseline 24-hour UPE  $> 1$  g/day) and in patients in the high-risk proteinuria group (baseline 24-hour UPE  $\geq 2$  g/day)

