Natural logarithm transformation will be used to analyze 24-hour UPE, 24-hour uPCR, 24-hour uACR, spot-urine uPCR, and spot-urine uACR. Geometric-mean ratio relative to the study baseline will be presented by treatment group and visit for the FAS population. A repeated measures model for the change in the log-transformed value from baseline will be used for analysis. The model will include treatment, time (as a categorical variable for the regular scheduled visits), treatment by time interaction, randomization strata as fixed effects, a time-dependent covariate for open-label treatment of narsoplimab as fixed effects, and an AR(1) covariance matrix. The time-dependent covariate is a binary variable that has a value of 0 before the initiation of the open-label treatment and 1 afterwards. It is defined for the placebo-treated group only. The REML method will be used to estimate the model parameters. The difference in LS means between the treatment groups and their respective 95% CIs will be estimated for each post-baseline scheduled visit. The LS mean will be estimated with 95% CI for each treatment group. The ratio of the GMR between the treatment groups will also be estimated with 95% CI. It is noted that the primary analysis of 24-hour UPE is based on the 24-hour UPE up to Week 36 and the time-dependent covariate is not applicable to the primary analysis.

Time-adjusted AUC change from baseline in log-transformed 24-hour uPCR through 36 weeks will be calculated as the AUC of the change from baseline in log-transformed 24-hour uPCR divided by the time from baseline to the last observation on or before Week 36. All 24-hour uPCR values collected from baseline to Week 36, including values collected at additional treatment visits and unscheduled visits, will be used to calculate the time adjusted AUC. Time

adjusted AUC of change in log-transformed 24-hour uPCR will be summarized descriptively. An analysis of covariance with treatment and randomization strata as factors and baseline uPCR as a covariate will be performed. The binary endpoints will be summarized descriptively. Non-responder imputation will be used to impute missing data. Exact 95% confidence intervals for the crude rate will be calculated and a Cochran–Mantel–Haenszel test stratified by the randomization stratum will be performed for the FAS population.

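### Protocol 14.1.10.3 time-averages spot-urine uPCR by ANOVA, while the listed endpoint and the SAP use log-transformed 24-hour uPCR with a baseline-adjusted ANCOVA

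*Protocol*

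**What the plan says.** The endpoint lists agree with one another. Protocol 7.2.4 gives, for the high-risk group, "Time-averaged change from baseline in the log-transformed 24-hour urine protein/creatinine ratio (uPCR) through 36 weeks", and the Synopsis gives the all-patients counterpart, "Time averaged change from baseline in the log-transformed 24-hour uPCR through 36 weeks in the all-patients population". The SAP's tertiary endpoints name the same variable: "Time averaged change from baseline in the log-transformed 24-hour uPCR through 36 weeks in patients in the high-risk proteinuria group".

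The analysis texts do not agree. SAP 2.9.2.4 analyses the "Time-adjusted AUC change from baseline in log-transformed 24-hour uPCR through 36 weeks" by analysis of covariance with treatment, strata and baseline uPCR. It counts readings from additional-treatment and unscheduled visits. Protocol 14.1.10.3 has instead: "Time adjusted AUC change from baseline in spot-urine uPCR through 36 weeks will be calculated as the AUC of the change from baseline". Its model is: "An ANOVA model with treatment and randomization strata as covariates will be performed". That paragraph does not say which visits count, and it does not mention the log scale. Earlier in the same section, however, there is a general statement: "Natural logarithm transformation will be used to analyze 24-hour UPE, 24-hour uPCR, 24-hour uACR, spot-urine uPCR and spot-urine uACR".

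**The concern.** No endpoint list contains a time-averaged spot-urine uPCR. Within the protocol, the described time-average belongs to no endpoint, and the listed time-average has no matching analysis. The specimen, the covariate set and the rule on included readings all differ from the SAP, and the scale is unclear.

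The specimen matters most, because spot and 24-hour urine are collected at different times. Spot samples cluster in the dosing weeks, and most 24-hour samples come later. A time average through Week 36 therefore gives the on-treatment and post-treatment periods different weight according to which series is used. At stake is which number is reported for this supportive endpoint, in both populations.

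**Working it through.** The plan gives no effect size, power or expected value for this endpoint, so there is no stated figure to reproduce. The check compares the weights that each schedule implies.

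**Inputs**
- Spot uPCR: T4 and T8 only between T2 and T11 (Protocol 20.2.1 footnotes), T12 (10.2.3.4), Week 36 (10.2.5.2), plus ExT4 if treatment is extended (20.2.2).
- 24-hour uPCR: one collection between T10 and T11 (10.2.3.4), Weeks 24, 30 and 36 (10.2.5), plus one between ExT5 and ExT6 if extended (20.2.2).
- Target days for T12 and Weeks 24, 30 and 36: 78, 162, 204, 246 (SAP 2.7, Table 2). Weekly dosing puts T4 on Day 22 and T8 on Day 50.
- Assumptions: trapezoid rule (neither document names one), change of zero at baseline, and ExT1 seven days after T12.

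**Formula.** With readings at times t over a window of length T, an interior reading has weight (next t − previous t)/(2T). The last reading has weight (t − previous t)/(2T).

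**Weights on nominal weeks, not extended**
- Spot, Weeks 0/4/8/12/36: 2, 4, 4, 14, 12 (each over 36). On-treatment share (4+4+14)/36 = 22/36 = 61%.
- 24-hour, Weeks 0/12/24/30/36: 6, 12, 9, 6, 3 (each over 36). On-treatment share 12/36 = 33%.
- On days, with the 24-hour sample at Day 68: 151/246 = 61% against 81/246 = 33%. A single line from Day 78 to Day 246 spans 168/246 = 68% of the spot window.

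**Weights on days, extended**
- Spot, Days 22/50/78/106: (25+28+28+84)/246 = 165/246 = 67%.
- 24-hour, Days 68/118: (59+47)/246 = 106/246 = 43%.

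**Effect on the estimate.** The weights were applied to assumed treatment-effect profiles, with full effect = 1 and both series on the same scale. The size of the effect cancels from the ratio. The last column repeats the calculation on study days, with the first 24-hour sample at Day 67.

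| Assumed profile (not extended) | Spot | 24-hour | Ratio, weeks | Ratio, days |
|---|---|---|---|---|
| Linear rise to Week 12, then sustained | 30/36 | 30/36 | 1.00 | 1.03 |
| Full by Week 4, sustained | 34/36 | 30/36 | 1.13 | 1.11 |
| Full Weeks 4–12, linear loss to zero at Week 36 | 22/36 | 18/36 | 1.22 | 1.20 |
| Full Weeks 4–12, a quarter left from Week 24 | 25/36 | 16.5/36 | 1.52 | 1.51 |
| Linear rise to Week 12, gone by Week 24 | 18/36 | 12/36 | 1.50 | 1.78 |
| Full Weeks 4–12, gone by Week 24 | 22/36 | 12/36 | 1.83 | 1.87 |
| None until Week 12, full by Week 24 | 12/36 | 18/36 | 0.67 | 0.64 |

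With extended treatment and an effect that lasts through dosing and is gone by Week 24, the ratio on days is 0.671/0.431 = 1.56.

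Neither series is uniformly closer to the underlying curve. In the second profile the true average is 0.944, which spot matches and the 24-hour series understates (0.833). In the sixth the true average is 0.444, which spot overstates (0.611) and the 24-hour series understates (0.333).

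**The case against.** The best defence is that this is stale wording with little consequence. Protocol 14.1.4 says that the protocol's statistical text summarises a fuller SAP. The SAP is to be final before the interim snapshot, and departures from it are to be justified in the study report. The SAP already analyses the listed endpoint. That endpoint is tertiary and outside type I error control (Protocol 14.1.6.3). All of this stands and sets the severity. It does not remove the contradiction: a summary may give less detail than the SAP, but here it names a different specimen and a different model. SAP Section 4, which records changes, does not mention the difference.

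Some stronger inferences are tempting but not supported:
- *The protocol prescribes the raw scale.* The paragraph omits the log, but the section's general statement applies the log to spot-urine uPCR. The scale is ambiguous, so an argument that the heaviest proteinuria would dominate cannot rest on this text.
- *The results will differ by 1.6- to 1.9-fold.* That needs an effect largely confined to the dosing weeks. The study rationale in Protocol 7.1 reports continued suppression after treatment, which points to the 1.0 to 1.2 range. The extreme case also meets the treatment rules. Taking the 35% UPE effect of Protocol 14.1.1 as an illustration, a 2 g baseline falls to 1.3 g, still above the 1 g criterion for extension. Losing that effect is a rise of 1/0.65 − 1 = 54% from the nadir, which meets the relapse definition. Retreatment adds spot samples at 6RT4 and 6RT6 and a 24-hour sample at 6RT6 (Protocol 20.2.4). Those samples were not modelled.
- *The definition could be chosen after unblinding.* Protocol 14.1.4 limits this risk, because the SAP is fixed before the interim snapshot.
- *Waning would be hidden.* The primary repeated-measures model uses Weeks 24, 30 and 36. Protocol 14.1.10.3 also plans a visit-by-visit model of 24-hour uPCR and durability AUCs for UPE.

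**Conclusion.** The point holds as a low-severity conflict between the protocol's analysis text and both its own endpoint list and the SAP. Specimen, covariate adjustment and included readings differ, and the log scale is left unstated.

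The weight difference follows from the sampling schedule and the trapezoid rule alone. The effect on the estimate depends on the time course. Across the profiles tried, the ratio ran from about 0.64 to about 1.9, and it stayed at about 1.0 to 1.2 for sustained or slowly waning effects. These profiles are assumptions, because the documents give none. The ratios also leave out retreatment samples and any systematic difference between spot and 24-hour measurements. No sample size, testing step, or primary or key secondary conclusion is affected.

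**What to change.** Replace the paragraph in Protocol 14.1.10.3 with the SAP 2.9.2.4 method: time-adjusted AUC of the change from baseline in log-transformed 24-hour uPCR through Week 36, analysed by ANCOVA with treatment, randomization strata and baseline uPCR. Carry over the SAP's rule on additional-treatment and unscheduled readings. Both documents then use the same weights, and the sampling-related ratio becomes 1.0.

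The spot-urine AUC need not be dropped, since spot uPCR is collected and Protocol 11.2 names uPCR alongside 24-hour uPCR as an efficacy measure. If it is wanted, list it as a separate exploratory endpoint on the log scale and state which visits enter it.

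The cost is protocol wording only. No new data or method is needed. The change is best made before the interim database snapshot.
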